6.2. Per protocol (PP) population

The per protocol (PP) population is a subset of the ITT population in which subjects will be excluded for, but not limited to, the following reasons:

- Missing consumption of product for two or more days during study product ingestion period
- Not consuming the study product the day before stool collection
- Missing appointments
- Use of prohibited drugs or any products thought to alter the primary outcome variable during the study
- Not adhering to instructions as outlined in the protocol

All decisions regarding the exclusions from the PP population will be documented following the data review meeting which will occur prior to database lock.

7. Determination of sample size

Sample size was determined based on previous studies, which indicate enrolling a sample size of N=25 will provide sufficient data for a significant effect. No subjects will be replaced in the event of early terminations.

8. Statistical methods

Unadjusted descriptive statistics will be provided per measured time point. Continuous variables will be summarized with mean, standard deviation, median, and range. Categorical variables will be summarized with counts and percentages. All tests of significance are two-sided and considered significant at the 0.05 level. SAS (version 9.4 or higher) or R (version 4.2.0 or higher) will be used for statistical analyses. All analyses will be conducted for the ITT and PP populations.

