8.2. Outcome analyses

For samples where LcS is not detected, counts will be set to the limit of detection to allow for statistical analysis¹. Descriptive plots will be provided for the distribution of LcS at each time point (i.e. boxplots) as well as line graphs for each subject. LcS number over time will be analyzed with a repeated measures model with an unstructured covariance structure where the LcS number at each time point will be included in the response vector. The model derived absolute change in LcS from baseline (day 14) to each of days 21, day 28, and 42 will be estimated along with the corresponding 95% confidence interval. In the event model assumptions are violated (i.e. constant variance and/or normality of residuals), a log transformation followed by a rank transformation will be considered. Note, if a rank transformation is used, contrast statements will be used to test the change from baseline but an estimate will not be calculated.

It is possible that the baseline LcS number for all subjects will be non-detectable which would likely result in the model assumption failure. If there are no detectable LcS levels at baseline and the repeated measure model assumptions are violated after exploring possible data transformations, then a model will be fit that only considers the post-consumption time points where the subject is on active product (day 21 and day 28). The estimated mean and 95% CI at day 21 and day 28 would then reflect an estimated increase from baseline. The proportion of subjects that return to baseline (day 14) by day 42 will be estimated along with a 95% CI. Additionally, in the subset of subjects that have elevated LcS while on study product measured at day 21 or day 28, as compared to baseline (day 14), the proportion of subjects that return to baseline by day 42 will be estimated along with a 95% CI.

Product emergent-AEs and SAE will be described. The proportion of subjects with at least 1 possibly, probably, or definitely related AE will be estimated along with the corresponding 95% CI.

9. Handling of missing data

For outcomes measured at multiple time points post baseline, statistical models that account for unbalanced data will be used. Specifically, missing data will be handled by maximum likelihood estimated of mixed models which assumes data is missing at random.

10. Deviations from statistical plan and other issues

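### SAP section 9 names maximum likelihood and no small-sample degrees of freedom for a model fitted to at most 25 participants; read literally, the 95% CIs are about 2% too narrow

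*SAP*

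**What the plan says.** SAP section 8.2 fits "a repeated measures model with an unstructured covariance structure" to the counts at days 14, 21, 28 and 42. The model-based change from day 14 "to each of days 21, day 28, and 42 will be estimated along with the corresponding 95% confidence interval". That section names no estimator.

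The only estimator named in either document is in SAP section 9, on missing data: "missing data will be handled by maximum likelihood estimated of mixed models which assumes data is missing at random". Protocol section 12.3.4 says only that the models will allow for unbalanced or missing data.

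SAP section 7 relies on the premise that "enrolling a sample size of N=25 will provide sufficient data for a significant effect", and adds that "No subjects will be replaced in the event of early terminations". The number analysed is therefore 25 or fewer. SAP section 8 sets the level ("All tests of significance are two-sided and considered significant at the 0.05 level") and the sets ("All analyses will be conducted for the ITT and PP populations"). It allows SAS or R, but gives no procedure, estimation option or degrees-of-freedom method.

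**The concern.** ML divides sums of squares by n and makes no allowance for having estimated the visit means. With hundreds of participants nobody would notice. With 25 or fewer, the standard errors are visibly too small, always in the direction that makes the result look more precise than it is. REML removes the bias and rests on the same missing-at-random assumption, so ML gains nothing here in handling missing data.

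A second gap sits beside the first. For a within-person contrast from n people, the reference distribution should have about n-1 degrees of freedom. If the software uses the residual count over all person-visits, or normal quantiles, the interval shrinks further.

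The main output of this single-arm study is an estimated change with a 95% CI, so the width of that interval is part of the result. SAP section 8.2 also compares day 42 with baseline. That difference may be small, and there a slightly inflated error rate could matter.

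**Working it through.** **Inputs.** n is at most 25 (SAP section 7); 4 visits with one mean each and an unstructured covariance (SAP section 8.2); ML (SAP section 9, read literally); two-sided 5% level (SAP section 8). The plan's N=25 cannot be reproduced, because neither document gives an effect size, SD, power or dropout rate. Sizes below 25 are assumptions that stand in for a reduced per protocol set.

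**Step 1: the ML effect alone.** With complete data, the ML covariance matrix is (n-1)/n times the unbiased sample covariance. Every contrast standard error, and so every CI width at a fixed critical value, is multiplied by sqrt((n-1)/n).

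- n=25: variance ratio 24/25 = 0.960; SE ratio sqrt(0.960) = 0.980.
- n=20: sqrt(19/20) = 0.975.
- n=18: sqrt(17/18) = 0.972.
- n=15: sqrt(14/15) = 0.966.

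The number of visits does not enter this ratio. A simulation with values missing completely at random after baseline (assumed SDs, correlation 0.5) gave SE ratios of 0.978 with 10% missing and 0.976 with 20% missing at n=25, against 0.980 with complete data. Fitting the unstructured matrix to incomplete data therefore adds little.

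**Step 2: coverage.** For normal residuals and complete data, the coverage of a nominal 95% interval with critical value c is P(|T| < c × r). T has n-1 degrees of freedom; r = sqrt((n-1)/n) for ML and r = 1 for REML. At n=25 the critical values are 2.064 for t(24), 1.985 for t(96) and 1.960 for the normal. The 96 is the residual count 4 × 25 - 4.

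| n=25 | REML coverage | ML coverage | ML width relative to REML with t(24) |
|---|---|---|---|
| t(24) | 95.0% | 94.6% | 0.980 |
| t(96) | 94.1% | 93.6% | 0.942 |
| normal | 93.8% | 93.3% | 0.931 |

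For smaller assumed sets, ML with t(n-1) covers 94.5% at n=20, 94.4% at n=18 and 94.3% at n=15. ML with normal quantiles covers 92.9%, 92.6% and 92.1%.

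**Step 3: separating the two effects at n=25.** Moving from REML to ML with t(24) costs 95.0 - 94.6 = 0.4 points. Moving from t(24) to normal quantiles under REML costs 95.0 - 93.8 = 1.2 points. The unstated degrees of freedom are the larger of the two.

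**The case against.** The ML wording stands in the missing-data section, where it explains why incomplete records can be kept. There it may loosely mean likelihood-based estimation, which includes REML. That reading is possible, and the SAP does not rule REML out. But ML is the only estimator named, and a programmer following the text would select it.

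The consequence also depends on the software. In one common R routine for this kind of model (gls), the reported standard error is rescaled by sqrt(100/96) for 25 people and 4 visits. Multiplied by sqrt(24/25), this is exactly 1.000, so no ML bias remains with complete data; only the degrees of freedom, 96 instead of 24, still shorten the interval. R is one of the two packages allowed, so the 2% is not certain to appear.

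The normal-theory coverages are themselves approximate here. Raw counts are skewed, and baselines may all sit at the limit of detection. SAP section 8.2 anticipates such failures with log, rank and post-baseline-only fallbacks, and these departures could move coverage more than ML does.

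Two stronger readings are tempting. A reader might infer that estimating a 4 by 4 unstructured matrix from 25 people causes the bias; Step 1 shows that it does not. A reader might also infer that the plan commits to intervals 6% or 7% too narrow. Those figures require a degrees-of-freedom choice that the SAP never states.

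**Conclusion.** The point holds as a minor correction. Taken at its word, SAP section 9 gives standard errors and CIs about 2% too narrow at n=25, with coverage 94.6% instead of 95%. With an assumed per protocol set of 15 to 20, the shortfall in width is 2.5% to 3.4%. This rests on complete data, normal residuals, t(n-1) and software that does not rescale the ML standard error.

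The open degrees of freedom could add more: coverage of 93.8% to 94.1% under REML and 93.3% to 93.6% under ML at n=25. That part is conditional on software the SAP leaves unspecified, so it is a gap in the plan and not a stated error.

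It does not follow that the primary conclusion is at risk. Protocol section 4.4 cites about 10^7 LcS per gram of feces after intake in earlier studies, and SAP section 8.2 expects that baseline may be undetectable in everyone. Against a rise of that size, a few per cent of CI width is unlikely to change the day 28 conclusion. What is affected is the reported precision and any small difference at day 42.

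**What to change.** In SAP section 9, replace the reference to maximum likelihood with: *restricted maximum likelihood (REML) with Kenward-Roger standard errors and degrees of freedom, valid under missing at random*. State that this applies to both the ITT and PP analyses, whichever of the permitted packages is used.

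The cost is one sentence and one software setting. Relative to ML with t(24), the CI at n=25 widens by 1/0.980 - 1, or about 2.1%; at an assumed n=15 it widens by about 3.5%. With complete normal data, REML with t(n-1) restores 95.0% coverage. It does not cure skewed counts or a baseline held at the limit of detection; those remain for the transformations and fallbacks in SAP section 8.2.
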